4.1.2. Per-Protocol Set for analysis of immunogenicity

The Per-Protocol set (PPS) for analysis of immunogenicity will be defined by time point (and this to include all eligible subjects' data up to the time of important protocol deviations). The PPS will include all evaluable subjects in the ES:

- Meeting all eligibility criteria.
- For whom the administration route of the vaccine was as according to protocol.

- For whom the study vaccine was administered as per protocol.
- Who did not receive a concomitant medication/ product leading to exclusion from a PP analysis, as described in Section 6.6.2 of the protocol, up to the considered time point.
- Who did not present with a medical condition leading to exclusion from a PP analysis, as described in Section 6.7 of the protocol, up to the considered time point.
- Who complied with the vaccination schedule, as specified in the protocol.
- Who complied with the timings of the post-vaccination blood sampling for immune response evaluation, as specified in the protocol.
- For whom post-vaccination immunogenicity results are available for at least one assay component at the corresponding time points.

4.2. Criteria for eliminating data from Analysis Sets

Elimination codes are used to identify subjects to be eliminated from analysis. Detail is provided below for each set.

4.2.1. Elimination from Exposed Set (ES)

Code 1030 (Study vaccine not administered at all) and code 900 (invalid informed consent or fraudulent data) will be used for identifying subjects eliminated from ES.

4.2.2. Elimination from Per-protocol analysis Set (PPS)

4.2.2.1. Excluded subjects

A subject will be excluded from the PPS analysis under the following conditions.

For codes 1040, 1070, 1080, 1090, 2040, 2060, 2080: subjects will be eliminated from a specific visit (at which the condition is met) onwards.

For codes 2090, 2100, 2120: subjects will be eliminated at the specific visit at which the condition is met.

Code	Condition under which the code is used	Visit (timepoints) where the code is applicable	Applicable for analysis set
900	Invalid informed consent or fraudulent data	All	All
1030	Study vaccine not administered at all	All	All
1040	Administration of concomitant vaccine(s) forbidden in the protocol: Any investigational or non-registered vaccine other than the study vaccine used during the study period A vaccine not foreseen by the study protocol administered during the period starting 30 days before the first dose and ending 30 days after the last vaccine dose, except for inactivated and subunit influenza vaccines which can be administered up to 14 days before or from 30 days after each vaccination.	All	Immunology
1050	Randomisation failure	All	Immunology
1060	Randomisation code was broken	All	Immunology
1070	Vaccination not according to protocol: Incomplete vaccination course Subject was vaccinated with the correct vaccine but containing a lower volume Wrong replacement or study vaccine administered (not compatible with the vaccine regimen associated to the treatment number) Route of the study vaccine is not intramuscular Wrong reconstitution of administered vaccine	All	Immunology
1080	Vaccine temperature deviation vaccine administered despite a Good Manufacturing Practices (GMP) no-go temperature deviation	Vaccination visits 1 and 4	Immunology
1090	Expired vaccine administered	Vaccination visits 1 and 4	Immunology
2010	Protocol violation (inclusion/exclusion criteria)	All	Immunology
2040	Administration of any medication forbidden by the protocol Any investigational or non-registered medication used during the study period Immunosuppressants or other immune-modifying drugs administered chronically (i.e., more than 14 consecutive days in total) during the study period Long-acting immune-modifying drugs administered at any time during the study period Immunoglobulins and/or any blood products administered during the study period	All	Immunology
2060	Intercurrent medical condition Subjects may be eliminated from the PPS if, during the study, they incur a condition that has the capability of altering their immune response or are confirmed to have an alteration of their initial immune status (other than RSV infection).	All	Immunology
2080	Subjects did not comply with vaccination schedule: Part A: number of days between dose 1 and dose 2 is outside [55-80 days] Part B: number of days between dose 1 and dose 2 is outside [55-75 days]	Visit 4	Immunology

Code	Condition under which the code is used	Visit (timepoints) where the code is applicable	Applicable for analysis set
2090	Subjects did not comply with blood sample schedule at a specific visit: Number of days between dose 1 and visit 3 blood sample is outside [30-37 days] Number of days between dose 2 and visit 6 blood sample is outside [30-37 days] Part B only: Number of days between dose 2 and visit 7 blood sample is outside [170-190 days] Number of days between dose 2 and visit 8 blood sample is outside [350-395 days]	Visits 3, 6, 7 and 8	Immunology
2100	Immunological results not available post-vaccination No immunological result at visit x for all 3 following tests: RSV A Neutralising antibody titer, RSVPreF3-specific IgG antibody concentration and RSVPreF3-specific CD4+ T cells frequency	Visits 3, 4, 6, 7, 8	Immunology
2120	Obvious incoherence or abnormality or error in data Unreliable released data as a result of confirmed sample mismatch or confirmed inappropriate sample handling at lab	Visits 1, 3, 4, 6, 7, 8	Immunology

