4. ANALYSIS SETS

4.1. Definition

4.1.1. Exposed Set

The Exposed Set (ES) will include all subjects with study vaccine administration documented.

A safety analysis based on the ES will include all vaccinated subjects.

An immunogenicity analysis based on ES will include all vaccinated subjects for whom immunogenicity data are available.

The ES analysis will be performed per treatment actually administered at Dose 1.

CONFIDENTIAL208851 (RSV OA=ADJ-002)
Statistical Analysis Plan Amendment 2**4.1.2. Per-Protocol Set for analysis of immunogenicity**

The Per-Protocol set (PPS) for analysis of immunogenicity will be defined by time point (and this to include all eligible subjects' data up to the time of important protocol deviations). The PPS will include all evaluable subjects in the ES:

- Meeting all eligibility criteria.
- For whom the administration route of the vaccine was as according to protocol.
- For whom the study vaccine was administered as per protocol.
- Who did not receive a concomitant medication/ product leading to exclusion from a PP analysis, as described in Section 6.6.2 of the protocol, up to the considered time point.
- Who did not present with a medical condition leading to exclusion from a PP analysis, as described in Section 6.7 of the protocol, up to the considered time point.
- Who complied with the vaccination schedule, as specified in the protocol.
- Who complied with the timings of the post-vaccination blood sampling for immune response evaluation, as specified in the protocol.
- For whom post-vaccination immunogenicity results are available for at least one assay component at the corresponding time points.

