5.3. Immunogenicity

5.3.1. Analysis of immunogenicity planned in the protocol

The primary analysis will be performed on the PPS for immunogenicity in Part A and Part B.

In Part B only: if in any study group the percentage of vaccinated subjects with serological results excluded from the PPS for analysis of immunogenicity is at least 10%, a second analysis will be performed on the ES.

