10.1.2.2. Laboratory data

Missing laboratory results (including immunological data) will not be replaced.

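### Code 2120 removes the whole subject at a visit from a per-protocol set shared by all assays, so a fault in one sample type also discards valid results from the other

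*SAP*

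**What the plan says.** All references are to the current SAP, Amendment 2. The sentence on code 2120 and its trigger read the same in the first version and in Amendment 1.

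- **One set, indexed by time point.** Section 4.1.2: "The Per-Protocol set (PPS) for analysis of immunogenicity will be defined by time point". Among its conditions is a subject "For whom post-vaccination immunogenicity results are available for at least one assay component at the corresponding time points". The set is not divided by assay.
- **What triggers code 2120.** The table in section 4.2.2.1: "Unreliable released data as a result of confirmed sample mismatch or confirmed inappropriate sample handling at lab". It applies to immunology as a whole, at Visits 1, 3, 4, 6, 7 and 8.
- **What follows.** "For codes 2090, 2100, 2120: subjects will be eliminated at the specific visit at which the condition is met".
- **The neighbouring code.** Code 2100, for unavailable results, requires "No immunological result at visit x for all 3 following tests": RSV-A neutralising titer, RSVPreF3 IgG and CD4+ T-cell frequency. It applies at Visits 3, 4, 6, 7 and 8.
- **Where the set is used.** Section 5.3.1: "The primary analysis will be performed on the PPS for immunogenicity in Part A and Part B". In Part B only, if the share of subjects with serological results in any group "excluded from the PPS for analysis of immunogenicity is at least 10%, a second analysis will be performed on the ES".
- **Missing results.** Section 10.1.2.2: "Missing laboratory results (including immunological data) will not be replaced".

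**The concern.** The trigger of code 2120 is a fault in a sample, but its consequence falls on a subject. The key to Figure 1 in section 2 lists separate blood samples for humoral and for cell-mediated responses, and section 5.3.1.2 measures the CD4+ response on PBMCs. A handling fault confined to one sample type is therefore possible by design, and the rule makes no allowance for it.

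What is lost is valid data on the secondary immunogenicity endpoints in their primary analysis. The ES analysis is only a partial remedy. It is not planned for Part A, and in Part B it depends on the 10% trigger. When it does run, no stated rule removes the unreliable result from it, because section 4.2.1 eliminates from the ES only under codes 900 and 1030.

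**Working it through.** The SAP states no figure on this point, so there is nothing to reproduce. The check has two parts: a comparison of the rules, and an illustration of size under assumed fault rates.

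**Comparison of the rules.** Take one subject at Day 91 with valid serum results, and vary only the state of the CD4+ result.

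| CD4+ result at Day 91 | Rule that applies | Serum results in the PPS at Day 91? |
|---|---|---|
| Valid | none | kept |
| Missing | code 2100 not met (two of three tests present) | kept |
| Released, but PBMC fault confirmed | code 2120, subject eliminated at the visit | lost |

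The serum results are equally good in all three rows. Section 4.2.2.1 contains only rules for excluded subjects, and no rule sets a single result to missing.

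**Size.** Inputs:

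- Part B group size is about 100 (about 70 aged 60-69 plus about 30 aged 70-80; section 2).
- The fault rate q per sample type and visit is not in the documents. I assume 1%, 3% and 5%.
- The standard error is taken as proportional to 1/√n, with the SD unchanged and faults unrelated to the response.

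*One sample type faulty at rate q.* The assays on the other type lose a fraction q of their results. The increase in SE is 1/√(1 − q) − 1:

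- q = 1%: 1/√0.99 − 1 = 0.5%
- q = 3%: 1/√0.97 − 1 = 1.5%
- q = 5%: 1/√0.95 − 1 = 2.6%

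*Both types faulty, independently, each at rate q.* Under the present rule every assay loses 1 − (1 − q)² of the group. Under a result-level rule it loses q. The avoidable part is q(1 − q).

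| q | Lost per 100, present rule | Lost per 100, result-level rule | Valid results lost per assay |
|---|---|---|---|
| 1% | 1.99 | 1 | 0.99 |
| 3% | 5.91 | 3 | 2.91 |
| 5% | 9.75 | 5 | 4.75 |

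The present rule roughly doubles each assay's loss. The ratio of the two SEs is √[(1 − q)/(1 − q)²] = 1/√(1 − q), so the increases are again 0.5%, 1.5% and 2.6%.

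*Relation to the 10% trigger.* For code 2120 alone to remove 10% of a group, with both types faulty independently, q must be 1 − √0.90 = 5.1% per sample type. Below that it only adds to exclusions made for other reasons.

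**The case against.** **Is this a contradiction in the SAP?** A reader might infer that code 2120 conflicts outright with code 2100 and with the criterion of at least one assay in section 4.1.2. The text does not support that. The criterion is one of several conditions for the PPS; meeting it does not guarantee inclusion. Code 2100 concerns absent results and code 2120 concerns released results confirmed to be wrong. Treating confirmed error more strictly than absence can be a deliberate, conservative choice. What stands is that the stricter treatment reaches results not shown to be wrong.

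**Is whole-visit elimination sometimes right?** Yes. Where a mismatch puts the identity of all the subject's samples at a visit in doubt, all results should go. A serum fault may also properly cost both serum assays. The point is limited to crossover between serum and PBMC.

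**Is the trigger narrow?** It needs a released result and a confirmed fault. A result that the laboratory never releases is simply missing, and the other assays are kept. This limits how often the rule bites, but not what it does when it applies.

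**Does a Visit 1 fault also cost the baseline?** A reader might infer that elimination at Visit 1 removes the unaffected assay's Day 1 value from fold increases and from the ANCOVA at later visits. The SAP does not say so. The set is defined by time point, elimination is at the specific visit, and the templates in section 12.3 count subjects with pre- and post-vaccination results available without requiring PPS membership at Visit 1. I therefore attach no figure to baseline loss.

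**Conclusion.** The point holds as a limited one. As written, code 2120 discards valid results of unaffected assays at the visit concerned, and no other section of the SAP narrows it. The size rests entirely on assumed fault rates: a 0.5% to 2.6% increase in SE for 1% to 5% of samples of one type affected at a visit. No bias between groups follows from the text.

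The conclusions are not threatened. The primary endpoints are safety endpoints analysed on the ES, and section 6 labels all comparisons exploratory. The change is worth making because it costs almost nothing and settles in advance which results survive a sample fault.

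**What to change.** In section 4.2.2.1, take code 2120 out of the sentence on elimination at a specific visit and add:

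> Under code 2120, only the result(s) from the affected sample at that visit, including Visit 1, are set to missing, and results of other assays from unaffected samples are kept. The subject is eliminated at that visit only if no reliable immunogenicity result remains, or if the mismatch puts the identity of all of the subject's samples at that visit in doubt.

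The wording should not hand the remaining cases to code 2100. That code does not apply at Visit 1 and looks at only three tests, so a subject whose only reliable result came from another assay would still be lost. If the rule is written for results and not only for PPS membership, the unreliable value can be left out of any ES analysis too. Codes 2090 and 2100 stay as they are.

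Cost: two sentences in the SAP and a result-level flag in the programming. No new data are needed.

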5. STATISTICAL ANALYSES

Note that standard data derivation rules and stat methods are described in “business rules document” and will not be repeated below. The study specific data derivation rules and stat methods will be described in section 9.

5.1. Demography

5.1.1. Analysis of demographics/baseline characteristics planned in the protocol

Demographic characteristics (age at first vaccination in years, gender, race and ethnicity) will be summarized by group using descriptive statistics:

- Frequency tables will be generated for categorical variable such as race.
- Mean, median, standard error and range will be provided for continuous data such as age.

The distribution of subjects will be tabulated as a whole and per group and for each age category (60-69 years and 70-80 years in Part B only).

Withdrawal status will be summarized by group using descriptive statistics:

- The number of subjects enrolled into the study as well as the number of subjects excluded from PP analyses will be tabulated.
- The numbers of withdrawn subjects will be tabulated according to the reason for withdrawal.

5.1.2. Additional considerations

The analysis of demographic characteristics by group will be performed on the ES and on the PPS.

Demography and baseline characteristics will also be summarized by country.

Vital signs (heart rate, respiratory rate, systolic/diastolic blood pressure, pulse oximetry) reported at visit 1 (Part A and Part B) will be summarized by group using descriptive statistics.

5.2. Exposure

5.2.1. Analysis of exposure planned in the protocol

NA

5.2.2. Additional considerations

The number of doses of study vaccines administered will be tabulated by group and by vaccine.

5.3. Immunogenicity

5.3.1. Analysis of immunogenicity planned in the protocol

The primary analysis will be performed on the PPS for immunogenicity and, if in any study group the percentage of vaccinated subjects with serological results excluded from the PPS for analysis of immunogenicity is at least 10%, a second analysis will be performed on the ES.

5.3.1.1. Within groups evaluation - humoral immune response

For each group, at each time point that blood samples are collected for humoral immune response and for each assay (unless otherwise specified):

In Part A and Part B:

- Percentage of subjects above pre-defined threshold and their exact 95% CI will be tabulated.
- GMCs/GMTs and their 95% CI will be tabulated and represented graphically.
- Geometric mean of ratios of antibody titer/concentrations at each post-vaccination time point over pre-vaccination (Day 1) will be tabulated with 95% CI.
- Antibody titer/concentration will be displayed using reverse cumulative curves.
- The ratio of fold increase (post over pre-vaccination) of RSVPreF3 ELISA antibody concentrations over the fold increase (post over pre-vaccination) of RSV-A and RSV B neutralizing antibody titers will be computed and tabulated using descriptive statistics.

In Part B only:

- The distributions of antibody titers/concentrations will be tabulated.
- Individual post-vaccination results (at Days 31 and 91) versus pre-vaccination results (Day 1) will be plotted using scatter plots. Results of the placebo group will be used as a reference.
- Distribution of the fold increase of the antibody titers/concentrations (post- over pre-vaccination titers) will be tabulated.
- The kinetics of GMT/GMCs will be plotted as a function of time for subjects with results available at all time points.

The immunogenicity analysis will also be performed by age category (age at Dose 1: 60-69 years and 70-80 years) in Part B only.

The humoral immune response by CMV status before vaccination might be explored in Parts A and B. This will be done if at least 10% of the subjects are included in each CMV status category (CMV positive and CMV negative).

5.3.1.2. Within groups evaluation - Cell-mediated immune response

The following parameters will be summarised by group using descriptive statistics (N, geometric mean [GM], min, Q1, median, Q3, max) at each time point during which blood samples are collected for CMI:

In Part A and Part B:

- Frequency of RSVPreF3-specific CD4+ T-cells identified as expressing **at least 2 markers** among IL-2, CD40L, TNF- α , IFN- γ , upon in vitro stimulation and background subtracted, measured by ICS using PBMCs.
- Frequency of CD4+ and/or CD8+ T-cells expressing **any combination of immune marker(s)** among CD40L, 41BB, IL-2, TNF- α , IFN- γ , IL-13, and IL-17, as measured by ICS using PBMCs (see details in section 5.3.2.2).

- Fold increase (post over pre-vaccination) of the frequency of RSVPreF3-specific CD4+ T-cells identified as expressing **at least 2 marker(s)** among IL-2, CD40L, TNF- α , IFN- γ , as measured by ICS using PBMCs.

In Part B only:

- Frequency of RSVPreF3-specific memory B-cells, as measured by ELISpot using PBMCs.
- Fold increase (post over pre-vaccination) of the frequency of RSVPreF3-specific memory B-cells, as measured by ELISpot using PBMCs.

This will be displayed overall and by pre-vaccination category: <Q1, Q1-Q3, >Q3, where Q1/Q3 are respectively the 25th and the 75th percentiles of the results at pre-vaccination computed on pooled groups.

In addition, vaccine response in terms of RSVPreF3-specific CD4+ T-cells expressing at least 2 markers among IL-2, CD40L, TNF- α , IFN- γ , will be explored and summarised by group.

The descriptive immunogenicity analysis will also be performed by age category (age at Dose 1: 60-69 years and 70-80 years) in Part B only.

The cell-mediated immune response by CMV status before vaccination might be explored in Parts A and B. This will be done if at least 10% of the subjects are included in each CMV status category (CMV positive and CMV negative).

5.3.1.3. Between groups evaluation (Part B only)

Statistical analyses will be performed to compare the 9 RSV investigational vaccine formulations in terms of RSV-A neutralizing antibody titers and RSVPreF3-specific CD4+ T-cells expressing at least 2 markers among IL-2, CD40L, TNF- α , IFN- γ .

The between-groups analysis will be performed using an ANCOVA model, in several steps as follows:

1. The 9 RSV formulations will be first compared to the Placebo in order to identify groups whose means are significantly higher from the mean of the Placebo group, in terms of RSV-A neutralizing antibody titers and RSVPreF3-specific CD4+ T-cells at Day 31 and Day 91 (One-sided alpha=2.5%, Dunnett's adjustment test for multiplicity).
2. The effect of the second vaccination will be evaluated by comparing the means one month post-Dose 2 (Day 91) and one month post-Dose 1 (Day 31), of the groups pooled according to their adjuvant content (AS01_B, AS01_E and Plain), in terms of RSVPreF3-specific CD4+ T-cells and RSV-A neutralizing antibody titers (One-sided alpha=2.5% for each superiority test: 2 doses > 1 dose).

Based on the results of this test, the next comparisons will be performed either at Day 91 or at Day 31.

3. Appropriate contrasts will be implemented to compare the RSV formulations as follows:
 - To demonstrate the adjuvant effect (on pooled groups according to their adjuvant content: AS01B, AS01E, Plain), by testing sequentially AS01B and AS01E versus Plain (One-sided alpha=2.5% for each superiority test: Adjuvant >Plain) in terms of RSVPreF3-specific CD4+ T-cells and RSV-A neutralizing antibodies and, if applicable, by comparing AS01B vs AS01E.
 - To demonstrate linearity of increase in immune response when increasing the antigen dose in each adjuvanted group in terms of RSV-A neutralizing antibody and/or RSVPreF3-specific CD4+ T-cells.
 - Further ANCOVA t-tests would demonstrate superiority of 120 µg or 60 µg, should a quadratic effect be demonstrated.
 - Similar exploratory comparisons might also be performed on the RSVPreF3 ELISA antibody concentrations if deemed necessary.

5.3.2. Additional considerations

5.3.2.1. Within groups – humoral immune response

- Correlations between assays of the humoral response will be investigated using scatter plots generated on pooled RSV groups:
 - RSVPreF3-specific IgG versus RSV A neutralizing antibody titer at each timepoint,
 - RSV A versus RSV B neutralizing antibody titer at Pre-vaccination and Day 91
 - RSVPreF3-specific IgG versus RSV-B neutralizing antibody titer at Pre-vaccination and Day 91

The same analysis will be performed on the fold increase post over pre-vaccination.

- The fold increase (post over pre-vaccination) of the RSVPreF3 IgG antibody concentrations versus the fold increase (post over pre-vaccination) of RSV-A and RSV B neutralizing antibody titers will also be displayed graphically by group using scatter plots.

